APPENDIX 6. SCHEDULE OF FOLLOW-UP ACTIVITIES

	Day										
	0	1	2	3	7	14	21	28	35	42	Any other
Procedure											
Clinical assessment	X	X	X	X	X	X	X	X	X	X	(X)
Temperature	X	X	X	X	X	X	X	X	X	X	(X)
Blood slide for parasite count	X		X	X	X	X	X	X	X	X	(X)
Urine sample	(X)										
Blood for:											
genotyping	X				X	X	X	X	(X)	(X)	X
haemoglobin or haematocrit	X					X		(X)		(X)	(X)
molecular markers	X				(X)	(X)	(X)	(X)	(X)	(X)	(X)
in vitro test	X										(X)
Treatment											
Medicine to be tested	X	X	X								
Rescue treatment		(X)	(X)	(X)	(X)	(X)	(X)	(X)			(X)

Parentheses denote conditional or optional activities. For example, treatment would be given on days 1 and 2 only for 3-day dosing. On day 1, the patient should be examined for parasitaemia if he or she has any danger signs or if parasite clearance needs to be calculated. Rescue treatment could be given on any day, provided that the patient meets the criteria for treatment failure. Extra days are any days other than regularly scheduled follow-up days when the patient returns to the facility because of recurrence of symptoms. On extra days, blood slides may be taken routinely or at the request of the clinical staff.

Day 0

Screening

- clinical assessment, including measurement of weight and height; referral in cases of severe malaria or danger signs;
- measurement of temperature;
- parasitological assessment;
- pregnancy test (if necessary);
- informed consent.

Enrolment

- treatment, first dose;
- blood sampling for genotyping.

Optional

- urinary test to detect antimalarial drugs;
- haemoglobin/haematocrit;
- molecular markers of drug resistance;
- in vitro test;
- antimalarial drug blood concentration.

Day 1

- clinical assessment; referral in cases of severe malaria or danger signs;
- measurement of axillary temperature;
- parasitological assessment in cases of severe malaria or danger signs or if parasite clearance needs to be calculated.;
- treatment, second dose or alternative treatment in case of early treatment failure.

Day 2

- clinical assessment; referral in cases of severe malaria or danger signs;
- measurement of axillary temperature;
- parasitological assessment;
- treatment, third dose or alternative treatment in case of early treatment failure.

Day 3, day 7, day 14, day 21, day 28, day 35 and day 42 and any other day ()

- clinical assessment; referral in cases of severe malaria or danger signs;
- measurement of axillary temperature;
- parasitological assessment;
- alternative treatment in cases of treatment failure;
- pregnancy test at the end of follow-up (if necessary);
- blood sampling for genotyping to distinguish between recrudescence and reinfection in cases of treatment failure after day 7 and in vitro susceptibility.

Optional (after day 7)

- haemoglobin/haematocrit;
- blood sampling for molecular markers for drug resistance

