5.2.9 Molecular markers for antimalarial drug resistance

Three drops of blood will be collected on a filter paper (3M Whatman filter) at day 0 and day of failure to define putative markers related to antimalarial drugs resistance (pfmdr1, pfprt, , cytb, pfmdr1 copy number, etc...), parasite genetic diversity and *Plasmodium* species. *Plasmodium* species will be determined using real time PCR (Chou et al, Malaria Journal 2012), genetic diversity using Nested PCR/gel migration (Leang et al, AAC 2012), bar coding (Hoyer et al, PlosOne 2012) and whole genome sequencing. Putative markers related to antimalarial drugs resistance will be analyzed by PCR/sequencing approach or by a multiplex real-time PCR assay (Leang et al, AAC 2012). Malaria Molecular Epidemiology laboratory at Institut Pasteur in Cambodia will be performing these tests. Specimens will be labelled anonymously (study number, day of follow-up, date), kept in individual plastic bags with desiccant pouches and protected from light, humidity and extreme temperature until analyzed. In order to identify whether Piperaquine is resistant blood spots at day 7 will be additionally collected with a special type of filter paper from every patients from all the study sites.

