5.2.10 Anti-malarial drugs blood concentration

By using the 100 ml capillary pipette, 100 ml capillary blood samples will be collected on day 7 for determining the blood concentration of piperaquine. The collected blood will be transferred on to the special filter paper (Watman ETCH31). Specimen will be labeled as follows: study number, day of follow up and date. Blood level will measured by using HPLC at Institute Pasteur in Cambodia.

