6.2 Follow-up

Patients who meet all the enrolment criteria will be given a personal identification number and will receive treatment only after the study has been fully explained to them and they have willingly provided informed consent. Any person who decides not to participate in the study will be examined, treated and followed-up by the health facility staff according to the standard of care established by the Ministry of Health.

The basic follow-up schedule is summarized in Appendix 6. A case report form (Appendix 7) and a serious adverse event report form (Appendix 8) will be used to record the general information and clinical observations on each patient enrolled into the study. The appointment schedule will be clearly explained, and a follow-up card with a personal identification number will be provided. House visits will be made in the event patient cannot make it to the clinic. If this is the case provide detail about the visiting staff and the study procedures that will be done at home. The health staff will send to the patient's residence and provides a transportation support for bringing the patient to the study site where he or she will receive the physical examination and laboratory test if necessary.

The day a patient is enrolled and receives the first dose of medicine is designated 'day 0'. All antimalarial treatment will be given by a study team member under supervision. Enrolled patients will be observed for at least 30 min after treatment to ensure that they do not vomit the medicine. If vomiting occurs within 30 min of treatment, the full treatment dose will be repeated. Ancillary treatment, such as antipyretics, will be provided if necessary to patients by the study team and documented on the case report form. Patients with persistent vomiting (i.e. necessitating more than a single repeat dose) will be excluded from the study and immediately referred to the health facility staff for appropriate management.

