Thereafter, patients are required to undergo regular clinical reassessment. Blood films for parasite counts will be made on days 2, 3 and 7 and then weekly for the remainder of the follow-up period, i.e. on days 14, 21, 28, 35 and 42. Patients will be advised to return on any day during the follow-up period if symptoms return and not to wait for the next scheduled visit day. In particular, parents or guardians should be instructed to bring children to the centre at any time if they show any sign of danger (unable to drink or breastfeed, vomiting everything, presenting with convulsions, lethargic or unconscious, unable to sit or stand, presenting with difficult breathing), if they are still sick or if there is any cause for worry. Clinical reassessment will be sufficiently thorough to ensure patient safety and will include assessment not only for potential treatment failure but also for potential adverse reactions to the medicine. Additionally, blood films will be obtained whenever parasitological reassessment is requested by the clinical staff.

Because many medicines have to be given over several days, the initial visits are critical not only for assessing efficacy but also for ensuring patient safety; defaulters at this stage will not have received a complete course of treatment and may be at risk for clinical deterioration. All reasonable efforts will be made to find defaulters to ensure complete treatment. Similarly, the ultimate success of the study rests on minimizing loss to follow-up. While patients are encouraged to return on their own for scheduled follow-up visits, it is essential that provisions be made ahead of time for locating patients at home if they do not attend as requested. This requires obtaining detailed directions to the home during enrolment, and study team members familiar with the community will be responsible for home visits and means of transport for the patients. The schedule of treatment and follow-up examinations given in this protocol must be followed to ensure data integrity. Patients who fail to return on days 1 and 2 and miss one dose of the treatment will be withdrawn from the study definitively. After day 3, patients who fail to return on day 7 but are present on day 6 or 8 (likewise days 13/15, days 20/22, days 27/29, days 34/36 and days 41/43) may still be included in the analysis. Deviation from the protocol of more than 1 day should, however, be avoided (see also section 3.7).

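### The drug-level blood sample is set for day 7 in section 5.2.10 but appears in Appendix 6 only as an optional day-0 item; day, status and analyte need reconciling together

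*Protocol*

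**What the plan says.** The protocol deals with this sample in five places.

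- **Section 2** lists blood concentration among the optional exploratory objectives. The drug name is still unfilled template text.
- **Section 5.2.9** (molecular markers) says, with piperaquine resistance as the purpose, that "blood spots at day 7 will be additionally collected with a special type of filter paper from every patients from all the study sites".
- **Section 5.2.10** says that "capillary blood samples will be collected on day 7 for determining the blood concentration of piperaquine", and continues: "The collected blood will be transferred on to the special filter paper". It names HPLC as the assay and the laboratory that will run it. Nothing there makes the sample optional.
- **Appendix 6** names "antimalarial drug blood concentration" once, as the last optional item for day 0.
- **Appendix 7**, day-7 case report form, has a collection box for the PCR sample and no field for a drug-level sample.

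On the standing of the schedule, section 6.2 says "The basic follow-up schedule is summarized in Appendix 6", and later: "The schedule of treatment and follow-up examinations given in this protocol must be followed to ensure data integrity".

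**The concern.** The body text and the schedule give different instructions for one sample, and they differ on both the day and the obligation. Field staff usually work from the schedule and the visit form, and neither would prompt a day-7 drug-level sample here.

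Appendix 6 puts study dosing on days 0, 1 and 2. A sample on day 0 therefore cannot reflect the completed course of any drug given in the study; at most it shows drug left from earlier treatment. A day-7 sample that is not taken cannot be recovered later. If some sites follow section 5.2.10 and others follow Appendix 6, the data will also differ between sites for reasons unrelated to patients or drugs.

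What is at stake is the optional exploratory objective on blood concentration, and no more than that.

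**Working it through.** The protocol states no figure to reproduce, so the check is a comparison of the passages.

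**Step 1: day and obligation**

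| Place | Day | Status | Analyte |
|---|---|---|---|
| Section 2 | not given | optional exploratory | unfilled |
| Section 5.2.9 (spot) | 7 | every patient, all sites | purpose is piperaquine resistance |
| Section 5.2.10 | 7 | directive | piperaquine |
| Appendix 6, table | no row | none | none |
| Appendix 6, day-0 list | 0 | optional | not named |
| Appendix 6, list covering day 7 | absent | none | none |
| Appendix 6, optional list after day 7 | absent | none | none |
| Appendix 7, day-7 form | no field | none | none |

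Section 5.2.10 and Appendix 6 cannot both be followed as written.

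**Step 2: could Appendix 6 imply the day-7 sample elsewhere?** The visit list that contains day 7 is headed "Day 3, day 7, day 14, day 21, day 28, day 35 and day 42 and any other day", and it has no drug-level item. The optional list after day 7 has haemoglobin or haematocrit and "blood sampling for molecular markers for drug resistance", again without drug concentration. In the table, the rows for blood are genotyping, haemoglobin or haematocrit, molecular markers and in vitro test. Day 7 carries a firm mark for genotyping and a conditional mark for molecular markers. The table therefore does record day-7 blood sampling, and the drug-level sample is not part of it.

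**Step 3: are the spots in 5.2.9 and 5.2.10 one sample?** Both are taken on day 7, both go on a special filter paper, and both concern piperaquine. Reading them as one sample is reasonable, but it is an inference. Only section 5.2.9 says every patient. The conflict over the day, between section 5.2.10 and Appendix 6, does not depend on this reading.

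**Step 4: what does a site following Appendix 6 collect?** It takes an optional day-0 sample, not labelled as pre-dose, or no sample at all. In either case it takes none after the course.

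**Step 5: would moving the day be enough?** The regimens are artesunate with mefloquine and artesunate with pyronaridine (section 4.1, Appendix 3). Piperaquine is in neither. A day-7 piperaquine level gives no exposure to the study drugs, so the analyte must be settled along with the day.

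**Step 6: upper bound on samples affected.** The synopsis plans 5 sites × 120 patients = 600. If every patient is meant and every site followed Appendix 6, up to 600 day-7 samples would not be taken. Losses, withdrawals and failures before day 7 would lower that number.

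**The case against.** The strongest reply is that little is lost. Blood concentration is optional and exploratory in section 2, is absent from the exploratory endpoints in the synopsis, and has no analysis in section 8.2. Section 6.2 calls Appendix 6 a summary of the basic schedule, and what it makes binding is the schedule given in the protocol, which includes section 5.2.10. The missing form box is weak evidence, because the forms have a collection box only for PCR: the in vitro sample has a firm day-0 mark in the table and no box on the day-0 form either.

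Most of this stands, and it keeps the point minor. It does not remove the conflict. A summary may omit detail, but this one places the sample on a different day and makes it optional.

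A reader might infer more: that sites would lose study-drug exposure data, so that late failures could not be separated into low exposure and resistance, for about 60 patients (600 × 10% planning failure rate). The documents do not support this. With piperaquine as the only named analyte, study-drug exposure is measured in nobody under either passage, so the 60 marks no difference between them. It also counts every failure, including early failures by day 3, who precede the day-7 sample. Nor do the documents say that sites would take a pre-treatment sample, since the day-0 entry is optional and not described as pre-dose.

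**Conclusion.** The inconsistency is real and minor. Section 5.2.10 directs a drug-level sample on day 7. Appendix 6 lists it only as optional on day 0, and neither the schedule nor the day-7 form prompts it after treatment. At any site working from Appendix 6, the exploratory blood-concentration objective could not be met. Primary efficacy, safety and sample size are unaffected.

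The consequence assumes that at least some sites work from Appendix 6 rather than section 5.2.10. The every-patient scope assumes that the spot in section 5.2.9 is the sample in section 5.2.10. Correcting the day is necessary but not sufficient: while piperaquine is the only named analyte, neither passage yields exposure to the study drugs.

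**What to change.** First decide whether the sample is wanted. Then make section 2, sections 5.2.9 and 5.2.10, Appendix 6 and the day-7 case report form agree on three things together: the day, whether the sample is mandatory or optional and for whom, and the analyte.

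If the sample is kept:
- fill in the drug name in section 2, and make the analyte in section 5.2.10 match it, with a stated reason if it is not a study drug;
- say whether the spots in sections 5.2.9 and 5.2.10 are one sample or two;
- add a day-7 drug-concentration row to the Appendix 6 table and a line to the list covering day 7;
- add a sample-collected box to the day-7 form;
- delete the day-0 entry, or label it as a separate residual-drug sample.

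If it is not kept, remove section 5.2.10, the Appendix 6 entry and the objective, and clear up the spot in section 5.2.9.

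The schedule and form changes cost one table row, one list line and one form box. No visit is added, because blood is already taken on day 7 for the slide and genotyping. Changing the analyte may affect the laboratory assay, and the documents do not allow that cost to be estimated.

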5.2.4 Microscopic blood examination

Thick and thin blood films for parasite counts should be obtained and examined at screening on day 0 to confirm adherence to the inclusion and exclusion criteria. Thick blood films will be also examined every 8 hours on days 1, 2, 3 and once on days 7, 14, 21, 28, 35 and 42 or on any other day if the patient returns spontaneously and parasitological reassessment is required. Specimens will be labeled anonymously (screening number or study number, day of follow-up, date). If this is a study to investigate parasitological response to a monotherapy with artemisinin-related compounds the number of parasite counts must be specified, e.g.: 2 thick blood films should be taken 12-hourly after screening for the 3 days or until parasite count is negative.

A fresh Giemsa stain dilution will be prepared at least once a day and possibly more often, depending on the number of slides to be processed. Giemsa-stained thick and thin blood films will be examined at a magnification of 1000 × to identify the parasite species and to determine the parasite density.

Three blood slides per patient will be obtained: two thick blood smears and one thin blood smear. One slide will then be stained rapidly (10% Giemsa for 10–15 min) for initial screening, while the others will be retained. If the patient is subsequently enrolled, the second slide will be stained more carefully (e.g. 2.5–3% Giemsa for 45–60 min), and slower staining will also be used for all slides obtained at follow-up visits. The study number of the patient, the date and the day of follow-up will be recorded either on the frosted edge of the slide or on the glass with a permanent glass pen.

The thick blood smear for initial screening will be used to count the numbers of asexual parasites and white blood cells in a limited number of microscopic fields. The adequate parasitaemia for enrolment is at least one parasite for every 16 white blood cells, corresponding to approximately 500 asexual parasites per microlitre for low-to-moderate transmission areas.

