5.2.5 Genotyping of malaria parasites

In order to differentiate a recrudescence (same parasite strain) from a newly acquired infection (different parasite strain), a genotype analysis will be conducted. This is based on the extensive genetic diversity among the malaria parasite genes *msp1*, *msp2* and *glurp 4*. The genotypic profiles of pre- and post-parasite strains are compared. The copy number of *P. falciparum mdr1* gene will also be measured as well as sequencing of Kelch gene.

In order to minimize discomfort to the patient due to repeated finger pricks, two to three drops of blood will be collected on filter paper Whatman 3MM during screening or enrolment and each time blood smears are required according to the protocol on and after day 7. Specimens will be labeled anonymously (study number, day of follow-up, date), kept in individual plastic bags with desiccant pouches and protected from light, humidity and extreme temperature until analyzed. When such room temperature conditions are not possible, for example in extremely humid environments where air-conditioning is not available, storage in a refrigerator or freezer will be considered, but great care will be taken to protect samples from frost and moisture. The PCR technique used will be performed by laboratory of Institute Pasteur in Cambodia. Paired filter papers will be used for parasite DNA extraction and genotyping. Unused filter papers will be kept in safe locations until data are eventually validated or for further research needs. All filter papers will be destroyed immediately after the PCR analyses have been completed. The sponsor will provide instructions to the principal investigator regarding shipment or destruction procedures of biological specimen collected during the study.

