8.2 Analysis of data

Standard WHO spreadsheet will be used for data management and analysis. Data will be analysed by two methods: the Kaplan-Meier method and per-protocol analysis. In addition to the reasons for withdrawal listed in section 3.8, patients will be considered withdrawn from the analysis if the PCR results are unclassifiable or if the results of PCR indicate that the failure is due to reinfection with *P. falciparum*.

The final analysis will include:

- a description of all patients screened and the distribution of reasons for non-inclusion in the study;
- a description of all the patients included in the study;
- the proportion of adverse events and serious adverse events in all the patients included in the study;
- the proportion of patients lost to follow-up or withdrawn, with 95% confidence intervals and a list of reasons for withdrawal;
- the cumulative incidence of success and failure rates at day 28 and 42, PCR-uncorrected and PCR-corrected; and
- the proportion of early treatment failure, late clinical failure, late parasitological failure and adequate clinical and parasitological response at day 28 and 42, with 95%

⁵ WHO/GMP. *Standardized data entry for therapeutic efficacy tests*. Geneva, World Health Organization (<http://www.who.int/malaria/resistance>).

confidence intervals, PCR-uncorrected and PCR-corrected.

Guidelines on calculating the cumulative success or failure rate, the proportion of adequate clinical and parasitological response and treatment failure are given in Appendix 9.

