APPENDIX 4. CLASSIFICATION OF TREATMENT OUTCOMES⁷

Early treatment failure

- danger signs or severe malaria on day 1, 2 or 3 in the presence of parasitaemia;
- parasitaemia on day 2 higher than on day 0, irrespective of axillary temperature;
- parasitaemia on day 3 with axillary temperature ≥ 37.5 °C;
- parasitaemia on day 3 $\geq 25\%$ of count on day 0.

Late treatment failure

Late clinical failure

- danger signs or severe malaria in the presence of parasitaemia on any day between day 4 and day 42) in patients who did not previously meet any of the criteria of early treatment failure;
- presence of parasitaemia on any day between day 4 and day 42) with axillary temperature ≥ 37.5 °C (or history of fever) in patients who did not previously meet any of the criteria of early treatment failure

Late parasitological failure

- presence of parasitaemia on any day between day 7 and day 42) with axillary temperature < 37.5 °C in patients who did not previously meet any of the criteria of early treatment failure or late clinical failure

Adequate clinical and parasitological response

- absence of parasitaemia on day 42), irrespective of axillary temperature, in patients who did not previously meet any of the criteria of early treatment failure, late clinical failure or late parasitological failure

⁷ WHO. *Susceptibility of Plasmodium falciparum to antimalarial drugs. Report on global monitoring 1996–2004*. Geneva, World Health Organization, 2005 (WHO/HTM/MAL/2005.110) (<http://www.who.int/malaria/resistance>).

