APPENDIX 8. GUIDELINES FOR ANALYSIS OF RESULTS

End-point for day X (X = 28 or 42)	PCR-uncorrected results	
	Cumulative success or failure rate (Kaplan-Meier analysis)	Proportion (per-protocol analysis)
Adequate clinical and parasitological response on day X	Success	Success
Early treatment failure	Failure	Failure
Late clinical failure before day 7	Failure	Failure
Late clinical failure or late parasitological failure on or after day 7	Failure	Failure
Other species infection	Censored day of infection	Excluded from analysis
Lost to follow-up	Censored last day of follow-up according to timetable	Excluded from analysis
Withdrawal and protocol violation	Censored last day of follow-up according to timetable before withdrawal or protocol violation	Excluded from analysis

End-point for day X (X = 28 or 42)	PCR-corrected results	
	Cumulative success or failure rate (Kaplan-Meier analysis)	Proportion (per-protocol analysis)
Adequate clinical and parasitological response at day X	Success	Success
Early treatment failure	Failure	Failure
Late clinical failure before day 7	Failure	Failure
Late clinical failure or late parasitological failure on or after day 7		

 • falciparum recrudescence* 	Failure	Failure

 • falciparum reinfection* 	Censored day of reinfection	Excluded from analysis

 • other species mixed with falciparum recrudescence 	Failure	Failure

 • other species mixed with falciparum reinfection 	Censored day of reinfection	Excluded from analysis

 • other species infection 	Censored day of infection	Excluded from analysis

 • undetermined or missing PCR 	Excluded from analysis	Excluded from analysis
Lost to follow-up	Censored last day of follow-up according to timetable	Excluded from analysis
Withdrawal and protocol violation	Censored last day of follow-up according to timetable before protocol violation or withdrawal	Excluded from analysis

* WHO. *Methods and techniques for clinical trials on antimalarial drug efficacy: genotyping to identify parasite populations*. Geneva, World Health Organization, 2008 (<http://www.who.int/malaria/resistance>)

NOTE:

COMBINED SITE

HC

COMBINDED HC

TRAPEANG CHO

ORAL

VEUNSAI

KACHUON HC & VIRAKCHEY

KEO SEIMA

SEN MONOROM

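### Three inconsistent rules for the PCR genotyping spot could leave some P. falciparum recurrences unclassified if a site follows Appendix 6 alone

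*Protocol*

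**What the plan says.** Three places in the protocol set the rule for the genotyping spot.

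- Section 5.2.5 takes it at screening or enrolment and then "each time blood smears are required according to the protocol on and after day 7".
- The table in Appendix 6 gives genotyping a plain X on days 0, 7, 14, 21, 28 and any other day, but (X) on days 35 and 42. Its note reads "Parentheses denote conditional or optional activities". The blood slide is a plain X on days 35 and 42.
- The list under the same table, for day 3 to day 42, asks for "blood sampling for genotyping to distinguish between recrudescence and reinfection in cases of treatment failure after day 7".

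The analysis side is set elsewhere. Appendix 4 defines late parasitological failure by "presence of parasitaemia on any day between day 7 and day 42" without measured fever. The PCR-corrected table in Appendix 8 (Guidelines for analysis of results) splits by PCR result every "Late clinical failure or late parasitological failure on or after day 7". Its row for "undetermined or missing PCR" is excluded from both the Kaplan-Meier and the per-protocol analysis. Section 8.2 agrees: "patients will be considered withdrawn from the analysis if the PCR results are unclassifiable". PCR correction applies to P. falciparum only (sections 2 and 3.1).

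**The concern.** The three rules differ both in the visits they cover and in what triggers the sample. Section 5.2.5 samples regardless of outcome. The Appendix 6 list samples only once a failure is recognised, and the table leaves days 35 and 42 to an unstated condition. Section 6.2 points sites to Appendix 6 for the follow-up schedule and says that the schedule must be followed, so staff who work from that appendix are following the protocol.

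A trigger that depends on failure is awkward here because failure is often not known at the finger prick. A late parasitological failure has no measured fever. Section 5.2.4 says that "slower staining will also be used for all slides obtained at follow-up visits", with 45 to 60 minutes given as the example, and two microscopists then read each slide independently, with a third if they disagree. The patient may have left by then.

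At stake is the PCR-corrected failure rate. Recrudescence and reinfection are told apart by comparing the enrolment sample with the recurrence sample. Without the second one, the patient leaves the analysis. If the recurrence was a recrudescence, the failure rate can only fall.

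**Working it through.** **Step 1. Set the rules side by side.**

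| Source | Day 7 | Days 14, 21, 28 | Days 35, 42 |
|---|---|---|---|
| Section 5.2.5 | every smear | every smear | every smear |
| Appendix 6 table | X | X | (X) |
| Appendix 6 list | omitted, read literally | failures only | failures only |
| Appendix 8 analysis table | PCR needed | PCR needed | PCR needed |
| Case report forms | prompt | prompt | prompt |

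No day is left out by all the sampling rules together. Day 7 is missing only from the list. Days 35 and 42 are weakened, not deleted, in the table, and the list covers failures on those days. The only rule that meets the analysis table on every day without needing to know the outcome is section 5.2.5.

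**Step 2. Reproduce the planned size (section 8.1).** Inputs: expected failure 10%, 95% confidence, precision 8 points.

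n = 1.96² × 0.10 × 0.90 / 0.08² = 54.02, stated as 54. With the 10% allowance, 54 × 1.10 = 59.4, rounded up to 60. Both figures reproduce. Expected failures among 54 are 0.10 × 54 = 5.4, so 5 or 6.

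**Step 3. Effect of lost recrudescences.** A failure with missing PCR leaves the numerator and the denominator. With F true recrudescences among n evaluable patients and k of them without a spot, the per-protocol estimate is (F − k)/(n − k). The value of k is an assumption, shown from 0 to 3, because the protocol gives no figure. Exact (Clopper-Pearson) 95% intervals are in brackets.

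| k | F = 5, n = 54 | F = 6, n = 54 |
|---|---|---|
| 0 | 5/54 = 9.3% (3.1 to 20.3) | 6/54 = 11.1% (4.2 to 22.6) |
| 1 | 4/53 = 7.5% (2.1 to 18.2) | 5/53 = 9.4% (3.1 to 20.7) |
| 2 | 3/52 = 5.8% (1.2 to 15.9) | 4/52 = 7.7% (2.1 to 18.5) |
| 3 | 2/51 = 3.9% (0.5 to 13.5) | 3/51 = 5.9% (1.2 to 16.2) |

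Before rounding, the step per lost recrudescence runs from 1.68 points (6/54 to 5/53) to 1.85 points (3/52 to 2/51), so about 1.7 to 1.9.

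**Step 4. Direction.** In the per-protocol analysis a reinfection is excluded anyway, so a reinfection without a spot changes nothing there. The estimate moves only when the missing spot belonged to a recrudescence, and then always towards better apparent efficacy.

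**The case against.** The strongest reply is that the protocol has several safeguards, and most of it stands.

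- Section 5.2.5 already states the full rule, and the table has a firm X on day 7.
- Section 5.2.9 separately takes a filter-paper sample on the day of failure.
- The case report forms for days 7, 14, 21, 28, 35, 42 and any other day all ask whether a PCR sample was collected.
- Section 5.1.1 gives every failure rescue treatment and follow-up until recovery, so the patient is seen again, and the table has a firm X for genotyping on any other day.

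A reader might therefore go too far in inferring that Appendix 6 leaves recurrences on days 7, 35 or 42 without a sample. The documents do not support that. A spot is lost only if a site works from one part of Appendix 6, reads it narrowly and overlooks the rest.

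Two further inferences also fail. Starting from 6/54, one lost spot takes the estimate from above to below 10%. But 10% is a planning value in section 8.1, not a decision threshold, and 5/54 is below it already. Nor does any figure in the protocol show that losses would fall mainly on days 35 and 42.

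The safeguards do not remove the inconsistency. The day-of-failure sample in section 5.2.9 also depends on failure being recognised. The form prompt records yes or no, and an answer of no on day 35 or 42 can comply with the table. The note to the table describes extra days as returns because of symptoms, which does not plainly cover an afebrile patient called back after a slide is read. The parentheses cannot simply mark the end of P. vivax follow-up at day 28, because the clinical, temperature and slide rows are all firm on days 35 and 42.

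**Conclusion.** The contradiction is real and should be corrected; the loss of data is possible, not built in. Its reach is limited to PCR-corrected P. falciparum results. P. vivax results are untouched, and so are the PCR-uncorrected results that section 8.2 also requires, where such a recurrence still counts as a failure.

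The size is about 1.7 to 1.9 points per lost recrudescence at one site. This assumes about 54 evaluable patients and 5 or 6 true recrudescences, with an unknown number of spots missed. That is small beside the planned precision of 8 points, but it runs in one direction, in a result meant to inform national treatment policy. This is a moderate consistency correction. It is best made before enrolment, because a missed spot may not be recoverable and no later analysis can replace it.

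**What to change.** Make Appendix 6 match section 5.2.5.

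- In the table, change genotyping on days 35 and 42 from (X) to X for P. falciparum patients.
- In the list for day 3 to day 42, replace the condition of treatment failure after day 7 with: *with every smear on and after day 7*.
- State that only the pairs from patients with a recurrence are assayed.

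The cost is two or three extra drops of blood at visits where the finger is already pricked for the smear, plus storage of filter papers that will mostly never be assayed. The sample size does not change.
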